## VARIABLES

Variable	Type	Description	Measurement
Treatment Groups: (Bimatoprost 0.01% with Mirtogenol ® or Bimatoprost 0.01% with Placebo)	Independent variable (Dichotomus)	Bimatoprost is a prostaglandin inhibitor used to lower IOP. Mirtogenol ® , a potent antioxidant and free radical scavenger supplement, or matching placebo to take daily in addition to bimatoprost.	Mirtogenol ® or Matching Placebo One capsule orally, once daily in the morning

Intraocular pressure	Dependent variable (Quantitative - Continuous)	The fluid pressure inside the eye created by the continual renewal within the eye.	Goldmann Applanation Tonometry
Visual acuity	Dependent variable (ordinal)	Measures the clarity of vision.	Snellen chart
Cup-to-disc ratio	Dependent variable (ordinal)	Measures the progression of glaucoma. Staging glaucomatous damage: Mild: <0.65 Moderate: 0.7-0.85 Severe: >0.9	OCT
Central Corneal Thickness	Dependent variable (Quantitative - Continuous)	Is the thickness of the cornea of the eye.	Pachymetry
Visual field changes	Dependent variable (Dichotomus)	Any type of visual field changes in the participants.	Perimetry
Adverse effects	Dependent variable (Dichotomus)	Adverse effects include: 
 
● Conjunctival hyperemia
 
● Periocular skin pigmentation
 
● Itching
 
● Eye irritation
 
● Foreign body sensation
 
● Growth of lashes
 
● Skin rash
 
● Headache
 
● Nausea
 
● Vomiting
 
● Diarrhea
 
● Dizziness (vertigo)
 
● Hyperglycemic episode
 
● Hypoglycemic episodes
 
	Patients will be questioned on the presence or absence of adverse effects.

		
 
● Bleeding
 
● Other
 
	
--	--	---	--

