The study will have five visits: screening and baseline, week 4, week 8, week 12 and week 24 of approximate 30-60 minutes of duration and an addition visit for pickup of the product after the randomization process. An ophthalmological evaluation will be conducted by a glaucoma specialist at each visit. At the baseline visit, the following tests will be performed: visual acuity, visual field evaluation, applanation tonometry, optical coherence tomography (OCT), and pachymetry. At week 4, and week 8 the following tests will be performed: visual acuity and applanation tonometry. At week 12, the following tests will be performed: visual acuity, visual field evaluation and applanation tonometry. At week 24, assessments will include the following: visual acuity, visual field evaluation, applanation tonometry, optical coherence tomography and pachymetry.

The same equipment will be used throughout the study for measurement consistency. Each test will be measured in the morning and the patient will be resting, sitting for at least 10 minutes before measurement. The tests will always be performed by the same person to rule out variations. At each visit, the IOP will be measured twice, with 10-minute intermissions between measurements, and mean values will be recorded. If only one eye is determined eligible as trial eye (meeting the diagnostic criteria for glaucoma), then all assessments will be performed only for the trial eye. If both eyes are eligible, only the eye with highest baseline mean IOP will be included in the statistical analysis. Patients will be instructed not to take any medications within two hours before measurements. Any therapy considered necessary for the patient's welfare will be given at the discretion of the treating physician and will be documented.

Safety measures include non-invasive techniques, standard of care treatment during the duration of the study, ophthalmological evaluations and assessment tests. Side effects or adverse effects will be reported and evaluated by the ophthalmologist at each visit and if deemed necessary the trial medication (Mirtogenol® or matching placebo) will be discontinued and therapy adjusted as

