## **STUDY SUBJECTS**

The data selection will be using a non-probabilistic sample with convenience sampling, preferably with a consecutive design. The individuals recruited will be Hispanic who receive services in a private ophthalmology glaucoma specialist office in San Juan, Puerto Rico.

Inclusion criteria include patients with:

1. Diagnosed with primary open-angle glaucoma (POAG)
2.  $\geq 21$  years old
3. Patient must be Hispanics (self-identified)
4. Current glaucoma treatment regimen of monotherapy with bimatoprost 0.01% administered into affected eye(s) once daily with stable IOP  $\leq$  of 21 mmHG

Exclusion criteria include patients with:

1.  $< 21$  year old,
2. Pregnant women or those who are planning to become pregnant in the next six (6) months,

3. Women who are breastfeeding,
4. Individuals with cardiovascular diseases that have required medical intervention in the past three (3) months,
5. Patients that required any kind of surgery, radiotherapy or chemotherapy in the past three (3) months,
6. Patients with advanced glaucoma with a cup to disk ratio  $> 0.9$ , previous glaucoma surgeries or other abnormalities of the eye that affect the visual pathway,
7. Patients with uveitis, diabetic retinopathy, macular edema or degenerative eye,
8. Patients with a history of adverse side effects of prostaglandin inhibitors,
9. Patients planning to undergo trabeculectomy or cataract surgery during the next six (6) months,
10. Patients using immunosuppressant therapy and anticoagulant,
11. Patients currently using Mirtogenol®.

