Both bimatoprost 0.01% and Mirtogenol® have been shown to have a good tolerability profile and a low incidence of side effects in previous studies. The risks and discomfort that may result because of this study are mild and minimal. Mirtogenol® contains bilberry and Pycnogenol® which may theoretically interact with immunosuppressive therapies and anticoagulant. Mirtogenol® may cause gastrointestinal discomfort, dizziness, headache and nausea. The ophthalmic solution of bimatoprost can cause an increase in the pigmentation of the iris, periorbital tissue (eyelid) and eyelashes, conjunctival hyperemia, conjunctival edema, conjunctival hemorrhage, eye irritation, eye pain, eye itching, eyelid sprain, pruritus eyelids, blurred vision and reduced visual acuity. All visual tests will be noninvasive, but some may cause discomfort and a small chance of cornea abrasion, which usually heals in a few days.

Benefits of the study may include intraocular pressure improvement, visual examinations and tests at no cost and the results of each test performed will be provided at the end of the study. The information in this research study may lead to better treatments in the future for people with glaucoma. Safety measures include non-invasive techniques, standard of care treatment during the duration of the study, ophthalmological evaluations, and assessment tests. Side effects or adverse effects will be reported and evaluated by a specialist and discontinuation of the trial medication will occur if deemed necessary by the treating ophthalmologist. Adverse effects will be documented at each study visit and the treating ophthalmologist will assess possible association of all adverse effects to the trial

medication. A visual acuity score indicating a loss of two or more lines or a cup to disk ratio from mild ( $<0.65$ ) to moderate ( $0.7-0.85$ ) or moderate to severe ( $>0.9$ ) will be considered relevant and a possible discontinuation of the study of participant from the study. Any changes in visual field, central corneal thickness or increase in IOP will be considered relevant and will be evaluated for a possible discontinuation of the participant.

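### The cup-to-disk stages leave two ranges of eligible values without a stage, and the cup-to-disk and corneal-thickness grounds for discontinuation have no scheduled reading before the final visit

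*Protocol*

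**What the plan says.** **Stages.** The Variables table in the protocol lists the cup-to-disk ratio as an ordinal dependent variable obtained by OCT. Its stated purpose is "Measures the progression of glaucoma", and its stages are "Mild: <0.65 Moderate: 0.7-0.85 Severe: >0.9".

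**Discontinuation text.** Under Study Subjects, the same cut-points define two moves, mild to moderate and moderate to severe. Either move, or a two-line loss of visual acuity, "will be considered relevant and a possible discontinuation of the study of participant from the study". The next sentence adds visual field, corneal thickness and a rise in IOP as matters to be evaluated for possible discontinuation.

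**Eligibility.** The exclusion criterion "Patients with advanced glaucoma with a cup to disk ratio" applies only to ratios above 0.9.

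**Schedule.** Methodology and Study Design lists these tests:
- Baseline: "visual acuity, visual field evaluation, applanation tonometry, optical coherence tomography (OCT), and pachymetry".
- Weeks 4 and 8: "At week 4, and week 8 the following tests will be performed: visual acuity and applanation tonometry".
- Week 12: "At week 12, the following tests will be performed: visual acuity, visual field evaluation and applanation tonometry".
- Week 24: "At week 24, assessments will include the following: visual acuity, visual field evaluation, applanation tonometry, optical coherence tomography and pachymetry".

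The Data Collection Form (Appendix, Table 2) agrees. It marks cup-to-disk ratio and corneal thickness as not applicable at weeks 4, 8 and 12.

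**Reporting.** The Analytic Plan includes change in cup-to-disk ratio in the safety analysis. The Safety Analysis table (Table 5) gives it a row under a heading for change in vision and progression, reported as number and percentage. No rule says what counts as a change.

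**The concern.** An ordinal scale used to record progression has to place every possible value in exactly one category. This one does not, and the unplaced values lie in the range that the trial admits. A patient who starts or ends in a gap has no defined stage, so a move between stages cannot be established for that patient. Site staff would have to leave the stage blank or push the value into a neighbouring stage, and the protocol gives no rule for either.

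Two uses are exposed. One is the stage-change ground for discontinuation, which is protocol content and is stated explicitly. The other is the cup-to-disk row of Table 5, if it is filled from stages.

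The schedule raises a separate question. A ground for stopping a participant is useful during treatment only if the measurement behind it is taken while treatment is still running.

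**Working it through.** The protocol gives no figure to reproduce here. The check applies the stated cut-points to the possible values, then sets the discontinuation text beside the schedule.

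**Step 1: which values have no stage.** With x the ratio, the stages are mild if x < 0.65, moderate if 0.70 ≤ x ≤ 0.85, and severe if x > 0.90. What remains is 0.65 ≤ x < 0.70 and 0.85 < x ≤ 0.90. The protocol does not state the recording precision, so three are shown:

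| Recording step | Values without a stage | Count |
|---|---|---|
| 0.01 | 0.65, 0.66, 0.67, 0.68, 0.69; 0.86, 0.87, 0.88, 0.89, 0.90 | 5 + 5 = 10 |
| 0.05 | 0.65; 0.90 | 2 |
| 0.10 | 0.90 | 1 |

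None of these values exceeds 0.9, so the cup-to-disk limit excludes none of them at baseline.

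**Step 2: the stage-change trigger applied literally.** It fires only on mild to moderate or moderate to severe.

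| Baseline to later value | Change | Stages | Fires? |
|---|---|---|---|
| 0.64 to 0.70 | +0.06 | mild to moderate | yes |
| 0.85 to 0.91 | +0.06 | moderate to severe | yes |
| 0.65 to 0.85 | +0.20 | none to moderate | no |
| 0.66 to 0.90 | +0.24 | none to none | no |
| 0.66 to 0.95 | +0.29 | none to severe | no |
| 0.86 to 0.95 | +0.09 | none to severe | no |

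**Step 3: is this due to the gaps, or to categorising at all?** Any categorical scale can register a small change across a boundary and ignore a larger one within a category, so the comparison of sizes alone proves little. The pair 0.66 to 0.95 is the clean test. Wherever in the lower gap the mild/moderate boundary is placed, 0.66 is either mild or moderate, and 0.95 is severe under the existing text. Every contiguous completion of the scale therefore shows a move of at least one stage, and the scale as written shows none. In steps of 0.05 the same holds for 0.65 to 0.95 (+0.30), while 0.60 to 0.70 (+0.10) fires. The other three misses in the table depend on where the boundaries are put.

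**Step 4: discontinuation grounds against the schedule.** Weeks 4, 8 and 12 are the three post-baseline visits before the last one.

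| Ground | Scheduled after baseline | Readings before week 24 |
|---|---|---|
| Cup-to-disk stage | week 24 | 0 of 3 |
| Corneal thickness | week 24 | 0 of 3 |
| Visual field | weeks 12, 24 | 1 of 3 |
| Visual acuity | weeks 4, 8, 12, 24 | 3 of 3 |
| IOP | weeks 4, 8, 12, 24 | 3 of 3 |

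Expected participation is 24 weeks. The first scheduled reading that could meet either of the first two grounds therefore falls at the end of participation.

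**The case against.** The strongest case on the other side accepts the gaps and the schedule but disputes what follows from them. Most of it stands.

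- **Discontinuation.** A reader might infer that the discontinuation rule cannot work. The documents do not support that. The text is discretionary, and its acuity, IOP and visual-field grounds all have scheduled readings during treatment. A glaucoma specialist sees the patient at every visit, and nothing forbids an unscheduled cup-to-disk reading. Even so, no such reading is listed and the form has no field for one, so the point about the two grounds remains.
- **Misclassification.** A reader might infer that patients are misclassified and that the Table 5 counts will be wrong. Values in the gaps are unclassified. They become errors only if they are rounded into a stage or counted as not progressed. No text says the Table 5 row counts stage moves, and it sits beside corneal thickness, which has no stages. Because the variable is called ordinal, a stage-based count is plausible, but it is not stated.
- **Size.** The ten unstaged values assume two-decimal recording. All the cut-points are multiples of 0.05, and on that grid only two values are affected. These are counts of possible readings, not of patients.
- **Importance.** The form has an entry for the ratio and the baseline table summarises it as mean (SD), so numeric values are evidently kept and a later definition would lose no data. The protocol plans no statistical testing of safety.
- **Analysis.** One might go on to ask that continuous change be made the main cup-to-disk analysis. That is a preference and corrects no error in the protocol.

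The objection does not remove the stated rule. A later analysis plan could define the Table 5 count, but discontinuation grounds and visit schedules belong to the protocol, and the protocol itself fixes the incomplete cut-points.

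**Conclusion.** The concern holds in a limited form. The cup-to-disk stages omit 0.65 to below 0.70 and above 0.85 to 0.90, all within the eligible range: ten values in steps of 0.01, two in steps of 0.05. Read literally, the stage-change ground misses a change such as 0.66 to 0.95, which any contiguous version of the scale would register, while it picks up 0.64 to 0.70. Table 5 is affected only on the assumption that its count uses stages.

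The cup-to-disk and corneal-thickness grounds have no scheduled reading at any of the three visits between baseline and week 24. That conclusion concerns scheduled tests and those two grounds only.

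How many patients would fall in the gaps cannot be derived from the protocol. The primary IOP comparison is not touched. This is a defect in a stated safety rule that should be corrected, and it does not threaten the trial's main conclusion.

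**What to change.** 1. Make the stages contiguous, so that every cup-to-disk value falls in exactly one. The clinical lead sets the boundaries; none is proposed here.
2. Use the same stages in the Variables table, in the discontinuation text under Study Subjects, and in any stage-based count in Table 5. If that row is not based on stages, say what counts as a change.
3. Reconcile the cup-to-disk and corneal-thickness discontinuation text with the test schedule in Methodology and Study Design. Which of the two should change is a clinical decision.

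Reporting the numeric change from baseline to week 24 beside the count is optional and uses values already collected. The cost is protocol wording only: no extra examination is requested and no clinical threshold is suggested.

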## ANALYTIC PLAN

A minimum sample of 72 participants will be used based on the primary efficacy endpoint of intraocular pressure to have an 80% probability to detect a difference between treatments at a two-sided 0.05 significance level. This is based on the assumption that the within-patient standard deviation of the response variable is 3.9 mmHg. Approximately 72 patients will be randomized in a 1:1 ratio to bimatoprost with Mirtogenol® or bimatoprost with placebo (intent-to-treat [ITT] population). There will be 36 patients enrolled in each population. Data will be presented as mean values with standard deviation to describe the population. The 95% confidence intervals assessments will be provided for descriptive purposes. The inferential statistical analysis to be conducted for the primary efficacy endpoint of IOP will be a t-test. All statistical tests will be performed with a significance level set at  $P < 0.05$ . The statistical software to be use will be Minitab. The safety analysis includes presence of adverse effects, changes in visual acuity, visual field, central corneal thickness and cup-to-disk ratio, but no correlation for multiple comparisons will be performed. The intention-to-treat method will be used where all participants who were randomized are included in the data analysis regardless of whether they received their assigned treatment for the entire study. Missing data will not be replaced, instead the last observation or value will be carried forward to account for patients who dropped out and for the statistical analysis.

**Sample Size:** We used the standardized effect size to estimate the sample size needed for the primary efficacy endpoint of IOP. The standardized effect size is the effect size divided by the standardized deviation of the variable. A previous study has reported that the mean on intraocular pressure in treated glaucoma patients is 15.1 mmHg, with a standard deviation of 3.9 mmHg. We would like to be able to detect a difference of 15% or more in the mean intraocular pressure between the two treatment groups. The effect size was calculated to be 0.39 and the standardized effect size is 0.60. Using a two-sided  $\alpha$  of 0.05 and power of 80%, the estimated sample size needed was 36 patients for each group, and 72 patients in total.

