## **HYPOTHESIS & SPECIFIC AIM**

The combination of Mirtogenol® and bimatoprost will have a superior reduction on intraocular pressure than bimatoprost with a placebo in Hispanic patients with primary open-angle glaucoma. Null hypothesis: The combination of Mirtogenol® and bimatoprost will have no difference on the reduction of intraocular pressure when compared to bimatoprost with a placebo in the Hispanic population with primary open-angle glaucoma (POAG). The specific aim of the study is to determine if the addition of Mirtogenol® to the bimatoprost 0.01% for open-angle glaucoma will have an additive effect on the intraocular pressure in the Hispanic population as compared to bimatoprost plus placebo. The continuous variable of intraocular pressure (IOP) will be compared

using a t-test to determine statistical significance. In addition, the safety of the combination of Mirtogenol® with bimatoprost will be evaluated, but no statistical analysis will be performed.

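### The protocol bases its 80% power on a within-patient SD that its own source describes as the spread of IOP between patients, and it never says whether IOP level or change is tested

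*Protocol*

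**What the plan says.** The first paragraph of the Analytic Plan promises a sample large enough "to have an 80% probability to detect a difference between treatments at a two-sided 0.05 significance level". It adds: "This is based on the assumption that the within-patient standard deviation of the response variable is 3.9 mmHg".

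The Sample Size paragraph of the same section gives the source of that figure: "A previous study has reported that the mean on intraocular pressure in treated glaucoma patients is 15.1 mmHg, with a standard deviation of 3.9 mmHg". The target is "We would like to be able to detect a difference of 15% or more in the mean intraocular pressure between the two treatment groups", and "The effect size was calculated to be 0.39 and the standardized effect size is 0.60". The result is 36 patients per group.

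The tested variable is worded in two ways. Under Hypothesis & Specific Aim, the combination "will have a superior reduction on intraocular pressure than bimatoprost with a placebo". The Research Question and the Background also speak of reduction. The aim, the endpoint statement under Methodology and Study Design, the Variables table, the t-test sentence in the Analytic Plan and the row of Appendix Table 4 (Week 12) all name IOP, with no mention of change from baseline.

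**The concern.** One number carries two meanings. A within-patient SD describes how one patient's readings vary from occasion to occasion. The SD around a mean IOP in a group of treated patients describes how patients differ from one another. The trial compares two parallel groups with a t-test. For IOP level, that test needs the between-patient SD of the level. For change, it needs the between-patient SD of the change. A within-patient SD is neither, so the description is wrong on either choice of variable.

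The unsettled variable adds to this. IOP is recorded at baseline and at each later visit, so both t-tests can be run on the same data. They will generally give different estimates, intervals and P values. The power also depends on which variable is meant, so the stated 80% cannot be checked until the variable and its SD are named together.

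**Working it through.** **Inputs, all from the Analytic Plan:** two-sided alpha 0.05; power 80%; 36 per group, 1:1; mean IOP 15.1 mmHg; SD 3.9 mmHg; target difference 15%; stated standardized effect 0.60. The baseline-to-follow-up correlation r is not given, so it is assumed and shown as a range.

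**Effect.** 0.15 × 15.1 = 2.265 mmHg, and 2.265 / 3.9 = 0.581. The protocol rounds this up to 0.60, which corresponds to 0.60 × 3.9 = 2.34 mmHg. So the protocol's own calculation uses 3.9 as the SD of the IOP level. The stated effect size of 0.39 fits neither 2.265 mmHg nor 0.60.

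**The stated sample size.** Normal approximation: n per group = 2 × (1.960 + 0.842)² / d².
- d = 0.60: 15.70 / 0.360 = 43.6, so 44 (45 by noncentral t).
- d = 0.581: 15.70 / 0.337 = 46.5, so 47 (48 by noncentral t).

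The stated 36 is not reproduced. A one-sided 0.05 test with d = 0.60 needs 35.04 by noncentral t, which rounds up to 36, but the protocol states a two-sided test. At two-sided 0.05, 36 per group needs a standardized effect of about 0.67.

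**Power for IOP level, between-patient SD 3.9, 36 per group.** Noncentral t with 70 degrees of freedom and noncentrality d × √(36/2):
- d = 0.581: noncentrality 2.46, power 68% (69% by normal approximation).
- d = 0.60: noncentrality 2.55, power 71% (72% by normal approximation).

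**Power for change from baseline, level SD 3.9 at both visits.** SD of change = 3.9 × √(2(1 − r)), difference 2.265:

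| Assumed r | SD of change (mmHg) | Power at 36 per group |
|---|---|---|
| 0.3 | 4.61 | 54% |
| 0.5 | 3.90 | 68% |
| 0.6 | 3.49 | 78% |
| 0.7 | 3.02 | 88% |
| 0.8 | 2.47 | 97% |

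For 80% power at 36 per group the SD must be 2.265 / 0.6696 = 3.38. Then r = 1 − 3.38² / (2 × 3.9²) = 0.62. The figure 3.9 is itself the SD of change only when r = 0.5.

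**If the label were taken literally.** With a within-patient SD of 3.9, the change between two visits has SD 3.9 × √2 = 5.52, and power is 40%.

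**The case against.** The strongest reply is that only one adjective is wrong. The operational text consistently names IOP: the aim, the endpoint, the Variables table, the target difference, the t-test and Table 4. For a t-test on IOP level, the SD of IOP across treated patients is the right kind of SD, and the protocol's 0.60 uses it that way. Reduction in the hypothesis is ordinary clinical language, because lower follow-up IOP in a randomized comparison is a usual way to show it. Finer detail on the variable could sit in a statistical analysis plan.

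Much of this stands. A reader might infer that the protocol defines its primary response as a reduction with a within-patient SD of 3.9, so that test and SD do not match. No section joins those two statements. On the level reading the source SD fits and the label alone is wrong. A reader might also take 40% as the trial's power, but that requires 3.9 to be truly within-patient, which the Sample Size paragraph contradicts. The 54% to 97% range rests on assumed correlations and on an analysis of change that the protocol does not specify.

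The reply does not rescue the power statement. The protocol itself fixes the test, the SD and the results table, describes that SD wrongly, and leaves level or change unsaid. On the reading most favourable to the 3.9, the 80% still does not follow.

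**Conclusion.** The point holds as an error in the stated basis for power together with an unnamed test variable. The 3.9 mmHg is called within-patient but is sourced as a between-patient SD of IOP level. For the level, which the operational text points to, 36 per group gives about 68% power at 2.265 mmHg and 71% at the stated 0.60. That shortfall comes from the sample-size arithmetic and not from the label. It appears once the variable and SD are correctly paired, so correcting the wording without restating the power would leave a wrong figure in place.

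This rests on the protocol's own description of the previous study, which is not at hand, on equal groups of 36 and on no loss to follow-up. The figures for change also assume the same SD at both visits and the correlations shown.

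**What to change.** 1. In the first paragraph of the Analytic Plan, replace within-patient standard deviation with between-patient standard deviation of IOP.
2. Name one tested variable in the same words under Hypothesis & Specific Aim, in the Analytic Plan and in Appendix Table 4. The operational text points to IOP at the primary visit.
3. Restate the power for that variable: for the level, about 68% at 2.265 mmHg or 71% at a standardized effect of 0.60.
4. If change from baseline is chosen instead, give the SD of the change, the assumed correlation and the reason for it. With a level SD of 3.9, about 80% power needs r of about 0.62. Relabelling 3.9 as the SD of IOP would not be enough, because it is the SD of change only at r = 0.5.

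The cost is wording in two sections and one table, with no new data or extra patients. The downside is a less favourable stated power. Choosing unadjusted change is a trade-off: it is less precise than the level when r is below 0.5, and the protocol gives no value for r.

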## **METHODOLOGY AND STUDY DESIGN**

A prospective, parallel-group, double-blind, randomized placebo-controlled clinical trial will be conducted with an estimated 72 primary open-angle glaucoma patients. A double blind RCT was chosen to minimize bias and yield similar groups with the same prognostic at baseline to avoid compromising the validity of the study results. The primary efficacy endpoint of the study will be IOP and the secondary endpoint will be the safety analysis. Qualifying participants will be evaluated for inclusion and exclusion criteria by their ophthalmologist ([name]) and informed about the study objectives. If they agree to participate, relevant baseline clinical data will be collected for each participant and they will be assigned to a treatment or a control group by stratified randomization based on their age, intraocular pressure and cup-to-disk ratio. This stratified randomization will allow comparability of randomized study groups at baseline. Participants will be randomized in a 1:1 ratio to treatment group (bimatoprost 0.01% and Mirtogenol®) or control group (bimatoprost 0.01% and placebo) and be assigned a participant ID number. Once the randomization process has concluded, participants will be notified to pass by the office to receive the product and to start using the Mirtogenol® or placebo the next day. Both Mirtogenol® and placebo bottles will label drug of study and be registered with a number identification for each patient. Mirtogenol and the placebo will be stored in a destined area in the

primary investigator's pharmacy under a cool, dry environment that protects them from extreme temperature changes and light. Oral and written instructions on drug regimen, including route of administration, frequency, proper storage and mode of administer will be provided. The groups will self-instill one drop of bimatoprost 0.01% in the affected eye(s) once daily as instructed by the ophthalmologist. In addition, participants will use one (1) capsule of Mirtogenol® or one (1) placebo capsule orally daily in the morning with food. Mirtogenol® will be funded by Life Extension Clinical Research, Inc. Placebo capsules will be similar in appearance, size, and route of administration to Mirtogenol®.

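### The primary IOP comparison is an unadjusted t-test although allocation is stratified on baseline IOP, age and cup-to-disk ratio; a baseline-adjusted ANCOVA would be more precise, by an amount the protocol does not let us fix

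*Protocol*

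**What the plan says.** The protocol names the primary test twice. Under Hypothesis & Specific Aim, IOP is to be compared "using a t-test to determine statistical significance". The Analytic Plan repeats it: "The inferential statistical analysis to be conducted for the primary efficacy endpoint of IOP will be a t-test". Neither place mentions a covariate or a stratification factor.

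Under Methodology and Study Design, participants are to be "assigned to a treatment or a control group by stratified randomization based on their age, intraocular pressure and cup-to-disk ratio". The same section has IOP measured before treatment: "At the baseline visit, the following tests will be performed: visual acuity, visual field evaluation, applanation tonometry". The Data Collection Form in the Appendix has entries for age, baseline IOP (two readings) and baseline cup-to-disk ratio.

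The hypothesis is worded as a "superior reduction on intraocular pressure than bimatoprost with a placebo". The sample-size text and Table 4 (Primary Efficacy Endpoint) refer to IOP itself. The design is meant to "have an 80% probability to detect a difference between treatments at a two-sided 0.05 significance level", and the sample-size paragraph takes it that "the mean on intraocular pressure in treated glaucoma patients is 15.1 mmHg, with a standard deviation of 3.9 mmHg".

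**The concern.** The design balances the arms on three baseline factors and the analysis then ignores them. Two things follow.

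- **Calibration.** If a balanced factor predicts follow-up IOP, the t-test's standard error still contains variation that the allocation has removed from the treatment comparison. The test then rejects less often than 5% under the null, and its confidence interval is wider than it need be.
- **Precision.** Baseline IOP is a measurement of the outcome variable on the same eye. Any correlation with follow-up IOP is information that the t-test discards.

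What is at stake is the width of the primary confidence interval and some power, in a trial of 72 patients. The hypothesis speaks of reduction while the tables speak of IOP, so it also helps to have an analysis that answers both wordings at once.

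**Working it through.** **Inputs from the protocol (Analytic Plan).** 36 per group; two-sided alpha 0.05; mean 15.1 mmHg; SD 3.9 mmHg; target difference 15%, so D = 0.15 × 15.1 = 2.265 mmHg. D/SD = 2.265/3.9 = 0.581; the protocol states 0.60.

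**Assumption.** The correlation r between baseline and follow-up IOP is not in the protocol, so it is varied from 0.2 to 0.7. The SD of 3.9 mmHg is read as the between-patient SD.

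**Step 1: the plan's own figure.** For the two-sided t-test at 36 per group:

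- SE = 3.9 × √(2/36) = 0.919 mmHg
- noncentrality = 2.265/0.919 = 2.464; critical t on 70 df = 1.994
- power (noncentral t) = 0.681, or 0.709 with the stated effect size of 0.60
- 95% CI half-width = 1.994 × 0.919 = 1.83 mmHg

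The stated 80% is not reproduced. Two-sided 80% power needs 45 per group at 0.60 or 48 at 0.581 (44 or 47 by the normal approximation).

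**Step 2: ANCOVA on baseline IOP.** Residual SD = 3.9 × √(1 − r²). All gain is credited to baseline IOP and none to age or cup-to-disk ratio. Power is the same to three decimals on 69 df (one covariate) or 67 df (three covariates).

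| r | residual SD (mmHg) | power | 95% CI half-width (mmHg) |
|---|---|---|---|
| t-test | 3.90 | 0.681 | 1.83 |
| 0.2 | 3.82 | 0.698 | 1.80 |
| 0.3 | 3.72 | 0.721 | 1.75 |
| 0.4 | 3.57 | 0.755 | 1.68 |
| 0.5 | 3.38 | 0.801 | 1.59 |
| 0.6 | 3.12 | 0.859 | 1.47 |
| 0.7 | 2.79 | 0.925 | 1.31 |

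Power reaches 80% at r of about 0.50 (D/SD = 0.581) or 0.44 (0.60). Half the shortfall is recovered at r of about 0.36 or 0.32. At r = 0.2 only 15% to 20% of it is recovered.

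**Step 3: how conservative the t-test is.** The protocol gives no stratum cut-points, so two equal baseline-IOP strata, balanced 18 and 18, were assumed and simulated. At r = 0.3, 0.5 and 0.7 the actual two-sided type I error of the t-test was about 0.045, 0.033 and 0.018. Under the same allocation its power was about 0.68, 0.69 and 0.71. The 0.681 in the table, which takes no account of the strata, therefore understates the t-test slightly at the higher correlations.

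**Step 4: final value or change.** With baseline IOP as a covariate, subtracting it from the outcome changes only the baseline coefficient, by exactly 1. The treatment estimate, its standard error and its p-value are unchanged. Without the covariate the choice matters: a t-test on change has SD = 3.9 × √(2(1 − r)) and power 0.602, 0.681, 0.775 and 0.880 at r = 0.4, 0.5, 0.6 and 0.7.

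**The case against.** The strongest reply is that nothing here is wrong. After 1:1 randomization the t-test estimates the treatment difference without bias, and ignoring the strata makes it conservative, so type I error is not inflated. The sample-size calculation is also a two-group comparison of means, so test and calculation match. This stands, and it makes the point a recommendation.

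A reader might infer from the table that ANCOVA would recover most or all of the missing power. The documents do not support that unconditionally:

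- The correlation is nowhere stated, and at 0.2 or 0.3 power is still only 0.70 or 0.72.
- Entry is limited to stable IOP of 21 mmHg or less, which narrows the baseline range and may lower the correlation.
- The Analytic Plan also says that "the within-patient standard deviation of the response variable is 3.9 mmHg". If that label were literal, between-patient variation would already be excluded and this gain could not be credited. The source given for 3.9, the spread of IOP among treated patients, points to the between-patient reading.

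A reader might also blame the t-test for the power shortfall. The shortfall comes from the sample size: with about 45 to 48 per group the same t-test would have 80% power.

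Lastly, one might infer that the protocol leaves a real choice between a change-score and a final-value t-test. The aim, the endpoint statement, the sample-size text and Table 4 all point to IOP itself, and no change-score test is specified. Reduction is the hypothesis wording, so the ambiguity is minor.

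**Conclusion.** The point holds as an efficiency recommendation. The planned t-test is valid. It is conservative after stratified allocation and less precise than a baseline-adjusted analysis whenever baseline IOP carries more than trivial information about follow-up IOP. Depending on a correlation that the protocol does not give, the gain runs from negligible (0.70 against 0.68 at 0.2) to large (0.93 at 0.7). These figures rest on 36 analysed per group, a 2.265 mmHg difference, 3.9 mmHg as the between-patient SD and a linear relation with baseline. No gain has been calculated for age or cup-to-disk ratio; they belong in the model because they are stratification factors. The sample-size statement needs its own correction whichever analysis is chosen.

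**What to change.** In the Analytic Plan, replace the t-test sentence with wording such as: The primary analysis will be an ANCOVA of IOP at the primary visit on treatment, with baseline IOP (continuous), age and cup-to-disk ratio as covariates; the adjusted mean difference will be reported with its 95% CI and two-sided p-value, and an unadjusted t-test will be supportive. Make the matching edit under Hypothesis & Specific Aim, and add that with baseline IOP in the model the treatment estimate is the same for IOP and for change from baseline, so it also tests the reduction hypothesis.

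The cost is one or two sentences, fixed before unblinding, and three degrees of freedom. No patient, visit or measurement is added. Correct the sample-size statement separately, because 36 per group does not give 80% two-sided power for the planned t-test at the stated inputs. If the revised calculation credits ANCOVA with a gain, state the assumed correlation and its source, and show power at lower values too.
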